#### **9.4.6 Laboratory Procedures/Assessments**

Details regarding specific laboratory procedures/assessments to be performed in this trial are provided below in Table 7.

Table 7 - Laboratory Tests

Hematology	Chemistry	Urinalysis	Other
Hematocrit	Albumin	Blood	Serum $\beta$ -human chorionic gonadotropin †
Hemoglobin	Alkaline phosphatase	Glucose	PT (INR)
Platelet count	Alanine aminotransferase (ALT)	Protein	aPTT
WBC (total and differential)	Aspartate aminotransferase (AST)	Specific gravity	Total triiodothyronine (T3)
Red Blood Cell Count	Lactate dehydrogenase (LDH)	Microscopic exam ( If abnormal )	Free tyroxine (T4)
Absolute Neutrophil Count	Carbon Dioxide	Urine pregnancy test †	Thyroid stimulating hormone (TSH)
Absolute Lymphocyte Count	Uric Acid		
	Calcium		
	Chloride		Blood for correlative studies
	Glucose		
	Phosphorus		
	Potassium		
	Sodium		
	Magnesium		
	Total Bilirubin		
	Direct Bilirubin ( If total bilirubin is elevated above the upper limit of normal )		
	Total protein		
	Blood Urea Nitrogen		
	Creatinine		

† Perform on women of childbearing potential only. If urine pregnancy results cannot be confirmed as negative, a serum pregnancy test will be required.

## 10.0 STATISTICAL ANALYSIS PLAN

### 10.1 Statistical Analysis Plan Summary

The rationale for combining radiation and immunotherapy has been written about extensively . However, these studies have focused on hypofractionated radiation in the metastatic setting and none of these published studies have examined the use of Pembrolizumab with the neoadjuvant radiation schedules that are typically used in the curative setting for many malignancies. Safety will be evaluated by CTCAE 5.0 and tabulated for qualitative description.

With regards to efficacy analysis, RECIST evaluations will be performed and tabulated in both qualitative and quantitative formats. This is a pilot trial that is not powered to give definitive determination of efficacy. As RECIST partial responses are not typically seen following neoadjuvant radiation alone, any objective responses would be highly interesting and encouraging of further study either for soft-tissue sarcomas generally or for a specific subtype where a response was observed.

The rate of complete necrosis will also be analyzed. It is assumed that the rate of complete necrosis in this subject population is approximately 15% after chemoradiation . A design with 26 subjects has 94.4% power to detect an improvement in the complete necrosis rate from 15% to 40%. The observation of at least 7 subjects with complete necrosis would be considered evidence to rule out a 15% complete necrosis rate. With 26 subjects, binary proportions can be estimated to within 20%. Any toxicity with at least 10% prevalence has at least a 94% chance of being observed.

Event free survival and overall survival at 1 and 5 years will be determined in order to estimate the potential benefit in the highest risk subjects. We will generate Kaplan Meier curves to illustrate these overall survival rates and event-free survival rates. Using data already being analyzed under IRB approved protocols, we will compare these to historical controls at our institution using Cox's proportional hazard model. Subjects' demographic variables (such as age and gender) will be incorporated in the analysis.

Biologic specimens will be compared using gene expression, flow cytometry and mIHC between pre and post treatment samples. This data will be utilized to quantify cellular infiltrates and create a detailed profile of T cell and macrophage phenotypes. For most samples, it is expected to obtain sufficient cell counts to flow sort live single cell suspension samples, CD45 neg (tumor) populations, and CD4+, CD8+ and CD11B+ populations for RNA extractions so that the RNAseq results on individual cellular populations may be compared.

The study center is experienced in expanding tumor infiltrating lymphocytes (TIL), and in most cases is able to expand TIL to numbers sufficient for functional assays. All tumor samples will be subject to TIL expansion. If tumors demonstrate defined immunogenic antigens, cytokine release assays will be performed to interrogate changes in T cell function

between pre and post treatment samples. If relevant, either expanded TIL or single cell suspension samples may be sent for TCR sequencing to determine how therapy impacts the TCR repertoire.

A historical series has been collected of such samples treated with radiation alone (protocol #9013) and the change in these two data sets will be compared using two-sample T-test. Pathway analysis tools (such as Gene Set Enrichment Analysis) may also be used to evaluate if relevant biological pathways (such as immun-response pathways) show any alterations with respect to the therapy. Kaplan Meier curves depicting genes of interest, mIHC results and clinical outcomes will be reported. Cluster analysis based on gene expressions may be performed, and followed by the conduct of subtype analysis, where appropriate. Gene expression's impact on the survival time will be evaluated, if appropriate, and its AUC (area under the curve) will be reported if such biomarkers show up in analysis.

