## **6.2 Rationale**

### **6.2.1 Rationale for the Trial and Selected Subject Population**

While a randomized trial would be required to definitively prove benefit of pembrolizumab in the neoadjuvant setting, this would require over 200 subjects and would likely take a year to accrue at 3-5 centers and would require years of follow-up for conclusive results. This

trial is proposed to estimate the potential benefit in the highest risk subjects. It is in such subjects that a prospective randomized trial could be conducted to detect benefit. Furthermore, sarcomas are superficial, allowing for easily accessible pre-treatment biopsies and are often very large (frequently >10 cm), allowing large tumor volumes to be available for correlative studies. This clinical situation offers a unique opportunity to study changes in tumor biology that may be applicable to all cancer types.

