#### **6.2.1.3 Rationale for the combination of Pembrolizumab and Neoadjuvant Radiation**

The rationale for combining radiation and immunotherapy has been written about extensively. However, these studies have focused on hypofractionated radiation in the metastatic setting. None of these published studies have examined the use of pembrolizumab with the neoadjuvant radiation schedules that are typically used in the curative setting for many malignancies (using high doses but in low-dose daily fractions). To more closely examine the expression of PD-1 and its ligand in the context of neoadjuvant treatment, we performed a retrospective study of sarcoma subjects who received neoadjuvant radiation where pre- and post-treatment tumor was available. While PD-1 and PD-L1 were similar following treatment, PD-L2 increased significantly ( $p < 0.05$ ), suggesting that blockade of PD-1 and PD-L2 might stimulate anti-tumor immunity leading to tumor

destruction and potentially the elimination of minimal residual disease.

[figure not shown]

Figure 3 - Gene expression based on a nanostring evaluation of sarcoma tumors before and after neoadjuvant radiation. PD1 (left) and PD-L1 (middle) were relatively unchanged following neoadjuvant radiation. However, PD-L2 (right) increased significantly  $p < 0.05$

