### **6.2.3 Rationale for Endpoints**

#### **6.2.3.1 Primary Endpoint**

Combining neoadjuvant radiation with pembrolizumab will likely have a higher rate of complete necrosis compared with historical controls. Complete or near-complete (>95%) necrosis after administration of neoadjuvant therapy is strongly associated with relapse-free survival prolonged in trials of chemotherapy combined with radiation of soft-tissue sarcoma. Rates of complete necrosis in trials with chemoradiation for soft tissue sarcoma are consistently <15%. Other small pilot trials of agents aimed at radiosensitization have also used complete necrosis as a surrogate for clinical activity. A significant improvement in the rate of complete necrosis would be a strong rationale to pursue a randomized trial of pembrolizumab combined with neoadjuvant radiation in the curative setting.

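### Does the success count of 7 in 26 (Section 10.1) conflict with the call in Section 6.2.3.1 for significance at no stated level?

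*Combined protocol and SAP*

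**What the plan says.** Section 10.1 sets the design for the primary endpoint with 26 subjects. The reference rate is stated as an assumption: "It is assumed that the rate of complete necrosis in this subject population is approximately 15% after chemoradiation". The alternative is 40%, the power is given as 94.4%, and the criterion is a count: "The observation of at least 7 subjects with complete necrosis would be considered evidence to rule out a 15% complete necrosis rate". The same section limits the claim: "This is a pilot trial that is not powered to give definitive determination of efficacy".

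Section 6.2.3.1, part of the rationale for the endpoints, looks ahead to the next step: "A significant improvement in the rate of complete necrosis would be a strong rationale to pursue a randomized trial". It does not mention the count of 7, and it attaches no significance level, sidedness or test to the word. Section 10.1 does not print a type I error or a confidence level for the count rule either. The p-values that the documents do print belong to background laboratory work (Sections 6.2.1.2 and 6.2.1.3), not to this endpoint.

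**The concern.** Read side by side, the two sections can look like two success criteria that part at the threshold itself. If significance in Section 6.2.3.1 means p < 0.05, as in the gene-expression comparison in Section 6.2.1.3, then exactly 7 of 26 satisfies the count in Section 10.1 but not the wording of Section 6.2.3.1 by an exact test. The plan would then give two answers on whether the result supports a randomized trial, which Section 6.2.1 puts at more than 200 subjects. In an open-label, single-arm study, an unstated level could also be chosen after the data are seen. And a report could claim that 15% is excluded beside a 95% interval that contains 15%.

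**Working it through.** **Inputs (all from Section 10.1).** n = 26; reference rate 15%; alternative 40%; success if X ≥ 7.

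**Step 1: reproduce the printed power.** With X binomial(26, p), P(X ≥ 7) = Σ C(26, k) p^k (1 − p)^(26 − k) for k = 7 to 26.
- At p = 0.40: 0.9441, which is the printed 94.4%. A normal approximation gives 92.0% at one-sided 5% and 95.2% at one-sided 10%. The printed figure therefore belongs to the exact rule with a count of 7.

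**Step 2: the error rate that goes with it.**
- At p = 0.15: P(X ≥ 7) = 0.0833. This is both the rule's type I error and the exact one-sided p-value at 7 of 26. The four stated inputs determine it, and no further choice is needed.

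**Step 3: how 7 of 26 (26.9%) reads under other conventions.**
- Exact two-sided p (summing outcomes no more likely than the one observed): 0.098.
- One-sided mid-p: 0.0321 + 0.5 × (0.0833 − 0.0321) = 0.058.
- One-sided score test: z = (0.2692 − 0.15) / √(0.15 × 0.85 / 26) = 1.70, p = 0.044. With continuity correction, p = 0.077.
- Clopper-Pearson two-sided 95% interval: 11.6% to 47.8%, which includes 15%. One-sided 90% lower bound: 15.7%, which excludes it.

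So 7 of 26 passes at one-sided 10% under every test listed. At one-sided 5% it passes only by the uncorrected score test.

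**Step 4: would a count of 8 settle it?**
- P(X ≥ 8) = 0.0321 at 15% and 0.8784 at 40%.
- The exact two-sided p at 8 of 26 is 0.047 by summing less likely outcomes, but 2 × 0.0321 = 0.064 by doubling.
- The Clopper-Pearson 95% interval is 14.3% to 51.8%, which still includes 15%.

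A count of 8 meets one-sided 5%, but it does not meet two-sided 5% under every standard exact convention.

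**Step 5: how often the boundary result occurs.**
- P(X = 7) at 15%: 0.0833 − 0.0321 = 0.0512.
- P(X = 7) at 40%: 0.9441 − 0.8784 = 0.0657.
- Share of false-positive successes that sit at exactly 7: 0.0512 / 0.0833 = 61.5%.

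**The case for a change.** The best case for a change is this. The plan quotes power to a tenth of a percent and speaks of ruling out a rate, yet omits the matching false-positive chance. Section 6.2.3.1 links the primary result to the next trial, so a reader is entitled to know what significance means there. The boundary result has a chance of 5% to 7% at the design's own two rates and makes up most of the false-positive successes. Wording in two sections would close the point at no cost in patients.

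Part of this stands. The 8.3% is not printed, and a reader who assumes 5% would be surprised by it. A report of 7 of 26 should show the exact p-value and interval beside the count.

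The rest does not carry. A second criterion appears only if the reader supplies a level, and the 5% would have to be borrowed from a retrospective PD-L2 comparison that has no bearing on this endpoint. The natural reading is that the statistical section defines what counts as improvement over 15%, and the rationale section refers to it in general terms. The threshold cannot drift after the data are seen, because the count is written down. Nor is the next trial made automatic: Section 6.2.3.1 calls the result a strong rationale, and the decision would be taken separately with all the data to hand.

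**Conclusion.** No change follows. The rule of at least 7 in 26 is fully specified in advance, its printed power is correct, and its type I error of 8.3% follows from the stated inputs. Writing that error down would leave the rule, the sample size and every planned estimate as they are. It is a missing label that an analyst supplies in one line.

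Moving to 8 in 26 would be a different design choice: error down from 8.3% to 3.2%, power at 40% down from 94.4% to 87.8%, a loss of 6.6 percentage points. Nothing in the documents requires that exchange. For a pilot that leaves definitive proof to a randomized trial, accepting a one-sided error just under 10% to keep power above 94% is a fair trade-off.

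This rests on three assumptions: 26 evaluable subjects, which the replacement provisions in Sections 7.2.3 and 7.5 are meant to secure; 15% as the fixed reference rate; and the exact binomial as the basis of the rule, which the reproduced 94.4% supports. Had the documents set a 5% level for this endpoint, 7 of 26 would miss it by the exact test and the conflict would be real. They do not.

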#### 3.1 Introduction

Although localized sarcoma is potentially curable, approximately 50% of subjects with large or high-grade tumors will ultimately develop incurable disease. This is a pilot study to examine the addition of the anti-PD-1 targeted, monoclonal-antibody pembrolizumab to standard, neoadjuvant radiation for subjects with high-risk soft tissue sarcomas planning for surgery with curative intent. Pembrolizumab has been combined in the past using hypofractionated radiation, but has never been combined with conventionally fractioned radiation with curative intent in soft tissue sarcoma subjects before. This trial will confirm the safety of this novel combination. A large randomized trial would be required to definitively demonstrate a relapse-free-survival benefit in this population. This study will instead focus on characterizing T-cell responses to this neoadjuvant combination, with a particular focus on the repertoire of tumor infiltrating lymphocytes (TIL). Tumor necrosis and radiographic response by RECIST criteria will be used as surrogates for efficacy, as has been done in other pilot trials combining radiation with novel therapies.

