#### 6.2.1.1 Neo-adjuvant Radiation for Soft Tissue Sarcomas

For subjects with small, low grade localized soft tissue sarcomas (STS), the combination of neo-adjuvant radiation and surgery can lead to excellent long-term disease free survival (DFS) rates of >80%. However, over one-half of subjects with a new diagnosis of localized STS will have larger, higher-grade tumors, approximately 50% of whom will develop fatal metastatic disease. Adjuvant and/or neo-adjuvant chemotherapy has been studied extensively, yet its role remains controversial. Practice patterns vary widely, to a large degree because the benefit is unclear and the agents used (doxorubicin and ifosfamide) are relatively toxic. Radiation for high-risk STS improves local control; at most sarcoma specialty centers, it is given preoperatively/neoadjuvantly. An agent with the potential to synergize with radiation and decrease the chance of metastatic spread would be highly desirable.

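### The exploratory Cox comparison of survival with historical controls names only demographic covariates, so smaller or low-grade tumours among the controls would bias the hazard ratio against the trial regimen

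*Combined protocol and SAP*

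**What the plan says.** Section 10.1 states that "Event free survival and overall survival at 1 and 5 years will be determined". It then commits to a comparison: "Using data already being analyzed under IRB approved protocols, we will compare these to historical controls at our institution", by Cox model. The adjustment follows in one sentence: "demographic variables (such as age and gender) will be incorporated in the analysis". No tumour factor is named for this model. No section gives eligibility, matching, weighting or an era for the survival controls. Later in section 10.1 a radiation-alone series (protocol #9013) is identified, but for specimen comparisons; nothing says that it supplies the survival controls.

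On prognosis, section 3.1 says that "approximately 50% of subjects with large or high-grade tumors will ultimately develop incurable disease". Section 6.2.1.1 gives long-term disease-free survival above 80% for small, low-grade tumours. For larger, higher-grade ones it says "approximately 50% of whom will develop fatal metastatic disease". Section 6.2.1.2 describes high-grade tumours as the most likely to spread.

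On selection, section 7.1.1 requires intermediate or high grade (criterion 5) and a minimum size of 3 cm or 1.5 cm respectively (criterion 6). It also admits localized recurrent and oligometastatic disease (criterion 4; see also the note to exclusion 8 in section 7.1.2).

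**The concern.** The protocol names its main prognostic factors and enrols on them, but leaves them out of the only adjustment it states for a non-randomized comparison. Age and gender cannot stand in for size and grade. If the historical series has a milder case mix, the model attributes the difference to treatment, so a real benefit could be hidden or a harm suggested where none exists. Section 10.1 says the survival analysis is meant to gauge possible benefit in the subjects at highest risk, and a comparison that does not hold risk constant answers that poorly.

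**Working it through.** **The plan's own figures.** None is given for this comparison: no HR, event count, control-series size, alpha or power. The only power figure, 94.4%, belongs to the necrosis endpoint. It reproduces, since the exact binomial P(X ≥ 7) with n = 26 and p = 0.40 is 0.9441, but it does not bear on this point.

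**Inputs.**
- Higher-risk event-free fraction 50% and lower-risk fraction 80% at one time point. These are assumptions prompted by sections 3.1 and 6.2.1.1. The protocol's figures are different outcomes (incurable disease, fatal metastasis, disease-free survival) without a common time point.
- All trial subjects at 50%, and no drug effect.
- Lower-risk share x among controls of 10%, 25% or 40% (assumed).
- 26 trial subjects (section 10.1) and 100 controls (assumed).

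**Bias.** The control fraction is S = 0.50(1 − x) + 0.80x. Under proportional hazards the apparent HR is ln(0.50)/ln(S), with ln(0.50) = −0.693.

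| x | S | ln S | Spurious HR | ln HR |
|---|---|---|---|---|
| 10% | 0.530 | −0.635 | 1.09 | 0.09 |
| 25% | 0.575 | −0.553 | 1.25 | 0.22 |
| 40% | 0.620 | −0.478 | 1.45 | 0.37 |

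With a lower-risk fraction of 70% or 90% instead of 80%, the 40% share gives 1.27 (S = 0.580) or 1.67 (S = 0.660).

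A Cox simulation with exponential times, 5-year censoring and 200,000 patients per series gave 1.09, 1.26 and 1.45 unadjusted, and 1.00 in each case once the risk group was in the model. Solving the large-sample Cox score equation also gave 1.25 at a 25% share.

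**Random error.** Take SE(ln HR) ≈ √(1/d₁ + 1/d₀), where d₁ and d₀ are the trial and control events, and place the 50% at 5 years with the same risk mix in both series.
- Five years: d₁ = 26 × 0.5 = 13 and d₀ = 50, so SE ≈ √(0.077 + 0.020) = 0.31 (simulated 0.32).
- One year: d₁ = 26 × (1 − 0.5^0.2) = 3.4 and d₀ = 12.9, so SE ≈ 0.61 (simulated 0.63).
- Two and a half years: d₁ = 26 × (1 − 0.5^0.5) = 7.6 and d₀ = 29.3, so SE ≈ √(0.132 + 0.034) = 0.41.

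At five years a shift of 0.37 exceeds one SE. At one year it is little more than half of one.

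**The case against.** Several objections have force.

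- **The controls are unseen.** They come from data held under other approved protocols, whose eligibility rules may already limit them to intermediate and high grade. If so, the bias illustrated above disappears. This stands: the imbalance is a possibility that the plan does not close off, and nothing in the documents shows that it exists.
- **The text does not limit the model to demographics.** Section 10.1 is a summary and says only that demographics will be included. That is fair, so a reader should not infer a decision to exclude tumour factors. But the list is open only to further demographic variables, and no other section supplies the missing terms.
- **Five-year data may not be reached.** Section 1.0 estimates a 3-year trial, although it also mentions follow-up to 5 years. Follow-up stops at the end of the study if that comes first (sections 8.1 and 9.3.6). One year is the time point in the objectives and endpoints (sections 4.3 and 5.3), and there noise dominates. This stands and lowers the value of any adjustment.
- **The perfect correction in the simulation is by construction.** It has one binary confounder measured without error. Restricting the controls would by itself remove the low-grade bias shown. What size and grade add afterwards, within the eligible range, is not quantified.

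A reader might also infer a false benefit of similar size by placing the 80% group in the trial. The documents do not support that. The 80% figure describes low-grade tumours, which criterion 5 excludes, and no section gives a better prognosis for any eligible subgroup. Bias in that direction is possible in principle, for example if the controls had larger tumours, but the documents give no figure for it.

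**Conclusion.** The point holds in a limited form. Following the stated adjustment would leave any size or grade imbalance in the HR. If the controls include smaller or low-grade tumours, the bias runs against the trial regimen: about 1.09 to 1.45 for shares of 10% to 40%, resting on the assumed 50% and 80% fractions, a trial series wholly at 50%, and no drug effect.

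The consequence is minor. Survival is exploratory, and section 10.1 says "This is a pilot trial that is not powered to give definitive determination of efficacy". Section 6.2.3.1 rests the case for a randomized trial on complete necrosis. No decision rule uses this HR, and the primary analysis is untouched. It is best treated as a cheap improvement.

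**What to change.** In section 10.1:

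1. Restrict the historical survival controls to patients who meet the trial's grade, size, subtype and disease-status criteria and who were treated with neoadjuvant radiation without systemic therapy. If the source protocols already impose this, one sentence saying so resolves most of the point.
2. Prespecify tumour size and grade as covariates, or grade as a stratum, alongside a small number of the planned demographic variables. With 26 trial subjects the model must stay small.
3. Tabulate size, grade and disease status for both series.
4. Report the HR with its confidence interval as descriptive.

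The cost is a few sentences plus chart extraction for the historical patients; size and grade are already needed for trial eligibility. The downside is fewer eligible controls and a slightly wider interval. For example, with 100 controls of whom 40% are lower-risk, 5-year control events are 60 × 0.5 + 40 × 0.2 = 38. After restriction they are 30. The SE moves from √(1/13 + 1/38) = 0.32 to √(1/13 + 1/30) = 0.33. Covariate adjustment without restriction cost the same in simulation (0.32 to 0.33).

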#### 6.2.1.2 PD-1 and PD-L1 Expression in Soft Tissue Sarcomas (STS)

We have seen T-cell tumor infiltration in a variety of sarcoma subtypes and the amount of infiltrating T cells has been associated with shorter disease specific survival, supporting the idea that checkpoint inhibition might be an effective strategy. One recent study found PD-1+ lymphocytes in 65% of STS tumors and PD-L1 expression by IHC in 58% of STS tested.

To better define the pattern of PD-L1 expression in specific STS subtypes, the [name] Lab entered into a collaboration with Merck to analyze 81 formalin-fixed, paraffin-embedded (FFPE) sarcoma samples from the University of Washington Tissue Bank for PD-L1 and PD-1 expression by IHC. Ninety percent of tumors tested positive for PD-1 staining and 59% for PD-L1. Significantly higher expression levels were seen in higher-grade tumors and pleomorphic undifferentiated sarcoma. Detectable PD-L1 was seen in a subset of each sarcoma subtype tested, including n=11 (58%) of leiomyosarcoma (LMS) and n=7 (47%) synovial sarcoma (SS). PD-1 expressing lymphocytes were also seen in a majority of tumors

[figure not shown]

Figure 2 - A) High PD-1 staining in a high grade, metastatic sarcoma. B) Profuse membranous tumor cell staining for PD-L1 in a leiomyosarcoma tumor. C) Levels of staining were scored by a pathologist experienced at interpreting PD-1 and PD-L1 staining (1 = focal, 2 >5%, 3 >25%, 4 >50%, 5 > 75%). Graph showing intensity of staining for individual sarcoma subtypes.

including n=16 (84%) LMS and n=15 (100%) SS. High (4+) or very high (5+) PD-L1 expression was seen in 10 sarcoma including 3 LMS (Figure 2). Seven tumors had high or very high PD-1 expression including one SS, and two LMS. In contrast, even though 100% of the SS tumors had some PD-1 expression, none of the SS tumors had either 4+ or 5+ PD-1 expression. Only n=4 (27%) of SS tumors had >2+ expression for PD-L1. Higher-grade tumors were associated with higher levels of both PD-L1 ( $p = 0.03$ ) and PD-1 expression ( $p = 0.05$ ).

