#### 7.1.1 Subject Inclusion Criteria

In order to be eligible for participation in this trial, the subject must:

1. Be willing and able to provide written informed consent for the trial.
2. Be  $\geq 18$  years of age on day of signing any informed consent documents.
3. Have measurable disease based on RECIST 1.1 criteria.
4. Have newly diagnosed disease or localized recurrent or oligometastatic lesions that are candidates for radiation.

- a. **NOTE:** Subjects may not have any prior systemic therapy or radiation for this sarcoma. They may have received systemic therapy and/or radiation for a different cancer.
- b. **NOTE:** Oligometastatic disease will be defined as 3 or fewer detectable lesions with plans to radiate all detectable disease with conventionally fractionated radiation prior to resection.

5. Have an intermediate or high-grade soft tissue sarcoma at the discretion of the reviewing Sarcoma pathologist.

6. The tumor must be at least 3 cm in maximum dimension for intermediate-grade tumors, or 1.5 cm in maximum dimension for high-grade tumors.

7. Have plans to undergo neo-adjuvant radiation and surgery with curative intent. A minimum of 45 Gy is necessary, planned to be administered over a minimum of 25 fractions.

8. Be willing to provide tissue from a newly obtained core, incisional or excisional biopsy of a tumor lesion. Archival tissue from a recent clinical or research biopsy (within 90 days prior to Week 1 treatment) may be used in place of a fresh tissue biopsy.

9. Have a performance status of 0 or 1 on the ECOG Performance Scale or >70% on the Karnofsky Scale. Evaluation of performance status is to be performed within 7 days prior to the date of enrollment.

10. Demonstrate adequate organ function as defined in Table 1. All screening laboratory tests should be performed within 28 days of enrollment.

Table 1 - Adequate Organ Function Laboratory Values

System	Laboratory Value
Hematological	
Absolute neutrophil count (ANC)	$\geq 1,500 / \text{mcL}$
Platelets	$\geq 100,000 / \text{mcL}$
Hemoglobin	$\geq 9 \text{ g/dL}$ or $\geq 5.6 \text{ mmol/L}^a$
Renal	
Serum creatinine OR Measured or calculated b creatinine clearance (GFR can also be used in place of creatinine or CrCl)	$\leq 1.5 \times \text{upper limit of normal (ULN)}$ OR $\geq 60 \text{ mL/min}$ for subject with creatinine levels $> 1.5 \times \text{institutional ULN}$

Hepatic	

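### The immune-change comparison with the radiation-alone series (#9013) has no control for grade or subtype, so a case-mix difference could be confounded with the pembrolizumab effect

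*Combined protocol and SAP*

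**What the plan says.** Section 10.1 (Statistical Analysis Plan Summary) compares biological specimens before and after treatment. It then brings in a historical series treated with radiation alone under protocol #9013 and states that "the change in these two data sets will be compared using two-sample T-test". It gives neither the size of that series nor its grade or subtype mix, and it names no covariate, matching or stratification for the test.

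Two other statements in Section 10.1 come close to adjustment but do not reach this test:

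- "Subjects' demographic variables (such as age and gender) will be incorporated in the analysis" stands in the paragraph on the Cox comparison of survival, and it concerns demographics, not tumour features.
- Subtype analysis is optional and follows clustering on gene expression.

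Section 6.2.1.2 reports PD-1 and PD-L1 staining in 81 archived sarcoma samples: "Significantly higher expression levels were seen in higher-grade tumors and pleomorphic undifferentiated sarcoma". It adds: "Higher-grade tumors were associated with higher levels of both PD-L1" (p = 0.03) and PD-1 (p = 0.05). Eligibility in Section 7.1.1 is broad: "Have an intermediate or high-grade soft tissue sarcoma at the discretion of the reviewing Sarcoma pathologist". New, localized recurrent and oligometastatic disease are all admitted.

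**The concern.** Section 3.1 puts characterisation of T-cell responses at the centre of the study. A pre-to-post change within the trial cannot isolate the drug, because radiation itself alters the markers. In the retrospective irradiated series of Section 6.2.1.3, "While PD-1 and PD-L1 were similar following treatment, PD-L2 increased significantly". The comparison with #9013 is therefore the only planned immune analysis that could separate the addition of pembrolizumab from radiation.

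The comparison is not randomised. If the trial and #9013 differ in grade or subtype, and those features influence how a marker changes under treatment, the t-test reports the sum of the drug effect and the case-mix effect. Nothing in the plan would separate the two or show the reader that they were mixed.

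**Working it through.** **The plan's own figures.** Section 10.1 gives no sample size, effect size or power for this comparison. Its one power figure, 94.4%, concerns complete necrosis (at least 7 of 26, 15% vs 40%). It reproduces at 0.9441 by exact binomial and has no bearing here.

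**What the protocol's data support.** The evidence in Section 6.2.1.2 concerns levels, not changes.

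- The subtype counts given do not differ clearly. For PD-L1, 11 (58%) leiomyosarcomas implies n = 19, and 7 (47%) synovial sarcomas implies n = 15; Fisher p = 0.73. For PD-1, 16/19 vs 15/15 gives p = 0.24.
- Dependence on subtype therefore rests on the statement about pleomorphic undifferentiated sarcoma.
- The section also conflicts with itself. It counts one synovial sarcoma among tumours with high or very high PD-1, then says none had 4+ or 5+ PD-1. This must be reconciled.
- The only change data (Section 6.2.1.3) are not broken down by grade or subtype.

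**Assumptions.** The documents do not describe #9013, so all of these are assumed: 26 subjects in each series, no drug effect, 70% vs 30% in the high-expression stratum, pre/post correlation rho of 0.3 to 0.5, and a two-sided 5% test. The unit is the within-stratum SD of a single measurement.

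**Step 1: only the level differs by stratum (1 SD).** The stratum term appears in both the pre and post values and cancels. In simulation the t-test on change has a type I error of 4.8%, so there is no bias.

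**Step 2: the change differs by stratum, by b SD.**

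- Spurious difference between series = (0.7 − 0.3) × b, which is 0.2 SD for b = 0.5 and 0.4 SD for b = 1.
- Variance of change within a series = 2(1 − rho) + 0.7 × 0.3 × b².
- Noncentrality = 0.4b / √(variance × (1/26 + 1/26)), with 50 degrees of freedom.

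| rho | b | Variance | Noncentrality | Type I error of t-test |
|---|---|---|---|---|
| 0.5 | 0.5 | 1.0525 | 0.70 | 10.6% |
| 0.5 | 1 | 1.21 | 1.31 | 25.1% |
| 0.3 | 0.5 | 1.4525 | 0.60 | 9.0% |
| 0.3 | 1 | 1.61 | 1.14 | 20.0% |

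Simulation at rho = 0.5 gives 10.3% and 25.2%; repeat runs of this setting reach about 26%. A linear model for change with a stratum term gives 5.3% in both cases.

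**Step 3: sensitivity.** With the SD of change within a stratum set to 1, the unadjusted rate runs from 5.7% to 48.9%. This range covers a historical series of 10 to 40, case-mix gaps of 20 to 40 points and b from 0.5 to 1.5.

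**Step 4: should the baseline value be in the main model?** Type I error in simulation, 26 vs 26, no drug effect, rho 0.3 to 0.5, baseline gap 0.5 to 0.8 SD:

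| Nature of the baseline gap | t-test on change | Change adjusted for baseline only |
|---|---|---|
| Transient (both series regress to one common mean) | about 15–39% | about 5% |
| Persistent (gap still present after treatment) | about 5% | about 17–47% |

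The ranking reverses with the nature of the gap. With a persistent gap, adding a stratum term that fails to capture it still leaves the baseline-adjusted model at 15–40%.

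**The case against.** The strongest defence is that the test is already on within-subject change. Grade and subtype are fixed tumour traits, and a level difference due to them can cancel, as Step 1 confirms. The documents do not show that change varies by grade or subtype, nor that #9013 differs from the trial in mix. The cited data cover PD-1 and PD-L1 staining only, while the comparison serves a wider set of markers. The endpoint is exploratory, in a pilot described as not powered for a definitive determination of efficacy, and no decision rule depends on this test. All of this stands, and it limits the point to a risk that the plan leaves uncontrolled.

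A reader might infer more: that any baseline difference between the series must create a spurious difference in change through regression to the mean, so that the t-test should give way to a baseline-adjusted model. The documents do not support this. It needs the baseline gap to be transient, and nothing in the documents says so. The gap suggested by Section 6.2.1.2 comes from tumour features that may well persist, and then baseline adjustment adds bias (Step 4). This is Lord's paradox, and in non-randomised groups neither analysis is right by default.

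The objection does not rescue the unadjusted test. Adjusting the change for grade and grouped subtype stayed near 5% wherever the case-mix factor drove either the level or the change.

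**Conclusion.** The point holds in a limited form. The planned t-test leaves grade and subtype uncontrolled in a non-randomised comparison, while the protocol's own data make both plausible confounders. Bias needs two conditions that the documents neither show nor exclude: a difference in case mix, and a change that depends on grade or subtype. If both hold to the extent assumed in Step 2, type I error is about 9% to 26% instead of 5%. Those figures are illustrative, because the size and mix of #9013 are not stated. The documents do not establish that a pembrolizumab effect reported from this test would be false. Priority is minor to moderate, since the endpoint is exploratory.

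**What to change.** In Section 10.1, make the main comparison a linear model for the pre-to-post change, on the log scale where suitable, with terms for series, grade and histologic subtype. Group the subtypes in advance so that the model stays sparse. Report the adjusted series effect with its confidence interval. Tabulate grade, subtype and baseline marker values for both series, so that a difference in mix is visible. Give the model that also includes the baseline value as a sensitivity analysis, and say that a discrepancy between the two reflects uncertainty about whether baseline gaps persist.

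The cost is a few sentences and a few degrees of freedom. With 26 vs 26, two grades and, say, three subtype groups, residual degrees of freedom fall from 50 to 52 − 5 = 47. Grade and subtype must be available for #9013, which the documents do not confirm. If they are not, the report should say that case mix could not be controlled.
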